1.0 Schema

2.0 Background

2.1 Chronic Lymphocytic Leukemia (CLL)

Chronic Lymphocytic Leukemia (CLL) is a malignancy of B-cells and is the most common form of leukemia in the western world, with an incidence of 3-5 per 100,000 (1). Although treatment options for CLL have expanded considerably in the recent years, it remains incurable. In the front-line setting, chemoimmunotherapy, in particular, the combination of rituximab with purine analogs and/or alkylator therapy, is one standard treatment for young and/or fit individuals with CLL who require treatment (2-4). Ibrutinib, a small molecule therapy that inhibits the tyrosine kinase Btk, is also an approved standard initial treatment for patients with CLL, with a high overall response rate of 89% (29% complete response) and 5-year progression-free survival of greater than 90% of patients who continue on ibrutinib (5-7).

There is not a standard of care therapy in the relapsed or refractory setting. Many patients cannot tolerate chemoimmunotherapy in that setting due to age, comorbidities, or compromised bone marrow function ^{4, 5}. Ibrutinib is an approved standard of care, though some comorbid conditions such as bleeding, requirement for anticoagulation, or heart disease may increase the risk of adverse events.

The combination of venetoclax and rituximab approved by the US FDA in 2018 as a standard treatment for patients with CLL who have received 1 prior therapy, regardless of cytogenetics or the specific prior therapy. Background regarding venetoclax follows.

2.2 Venetoclax

2.2.1 Venetoclax Overview

Venetoclax (VENCLEXTA[™]) is a potent, orally administered inhibitor of B-cell lymphoma 2 (BCL-2) co-developed by AbbVie Inc and Genentech Inc for the treatment of B-cell malignancies. Venetoclax has been approved in the US for the treatment of patients with CLL with 17p deletion, as detected by an FDA approved test, who have received at least one prior therapy.

The Bcl-2 family proteins are important regulators of the intrinsic apoptosis pathway. The Bcl-2 oncogene was first identified in follicular lymphoma (FL) where the t(14;18) chromosomal translocation results in significant over-expression of the protein in B-cells. The Bcl-2 family of genes encodes a family of closely related proteins that possess either pro-apoptotic or antiapoptotic activity and share up to four Bcl-2 Homology (BH) domains. Bcl-2 overexpression is a major contributor to the pathogenesis of some types of lymphoid malignancies. Bcl-2 is also overexpressed in acute and chronic leukemias. Chronic lymphocytic leukemia (CLL) is a genetic disease where the microRNAs miR15a and miR16-1 that negatively regulate the transcription of Bcl-2 are deleted or down-regulated, resulting in uncontrolled expression of Bcl-2.

Venetoclax (also known as ABT-199) is a novel, orally available, small molecule Bcl-2 family protein inhibitor that binds with high affinity (Ki <0.010 nM) to Bcl-2 and with lower affinity to other Bcl-2 family proteins Bcl-XL and Bcl-w (>4,000-fold and >2,000- to >20,000-fold lower affinity than to Bcl-2, respectively). Selective inhibition by venetoclax disrupts Bcl-2 signaling and rapidly induces multiple hallmarks of apoptotic cell death in Bcl-2- dependent human tumor cell lines (venetoclax IB).

2.2.2 Summary of Nonclinical Data

In vitro, venetoclax demonstrated broad cell killing activity against patient-derived CLL and acute myeloid leukemia (AML) cells, and a variety of lymphoma and leukemia cell lines including B-cell follicular lymphomas (FLs), mantle cell lymphomas (MCLs), diffuse large B-cell lymphomas (DLBCLs), AMLs, and multiple myeloma cell lines. Venetoclax was especially potent against cell lines expressing high levels of Bcl-2. A detailed discussion of the non-clinical toxicology, metabolism, and pharmacology can be found in the venetoclax IB.

2.2.3 Summary of Venetoclax Clinical Data

2.2.3.1 Clinical Pharmacokinetics

Following multiple oral administrations under fed conditions, maximum plasma concentration of venetoclax was reached 5-8 hours after dose. Venetoclax steady state AUC increased proportionally over the dose range of 150-800 mg.

Food can increase venetoclax exposure (3.4-fold with a low-fat meal and 5.1- to 5.3-fold with a high-fat meal). Venetoclax should be administered with a meal. The population estimate for the terminal elimination half-life of venetoclax was approximately 26 hours. In vitro studies demonstrated that venetoclax is predominantly metabolized by CYP3A4/5. Less than 0.1% of venetoclax is excreted renally.

Venetoclax exposures in subjects with mild or moderate renal impairment are similar to those with normal renal function. The pharmacokinetics of venetoclax has not been studied in subjects with severe renal impairment (CrCl <30 mL/min) or subjects on dialysis.

Venetoclax exposures are similar in subjects with mild and moderate hepatic impairment and normal hepatic function based on the NCI Organ Dysfunction Working Group criteria. Mild hepatic impairment was defined as normal total bilirubin and aspartate transaminase (AST) > upper limit of normal (ULN) or total bilirubin >1.0 to 1.5 times ULN, moderate hepatic impairment as total bilirubin >1.5 to 3.0 times ULN, and severe hepatic impairment as total bilirubin >3.0 times ULN. The pharmacokinetics of venetoclax has not been studied in subjects with severe hepatic impairment.

For the most comprehensive information regarding pharmacokinetics (PK) and product metabolism, please refer to the current version of the venetoclax IB.

2.2.3.2 Summary of Clinical Safety

Doses administered in venetoclax clinical studies have ranged from 20 mg to 1200 mg. As of 28 November 2015 and version 7 of the Investigator's Brochure, on the basis of data available in the AbbVie and Genentech/Roche clinical databases, a total of 1662 subjects have been exposed to at least 1 dose of venetoclax in the oncology and immunology development programs. A total of 1493 oncology subjects have data available in AbbVie and Genentech/Roche studies as of 28 November 2015. Of these 1493, there are 935 subjects with CLL/ SLL, 346 subjects with NHL, 110 subjects with MM, 102 with AML. An additional 66 subjects are healthy volunteers. A total of 560 oncology subjects received the drug as monotherapy, 933 have received the drug in combination with other therapies, and 1 subject received venetoclax as a single dose in a drugdrug interaction study and did not re-enroll into a subsequent monotherapy study. Additionally, 98 subjects have been exposed to at least 1 dose of venetoclax in the AbbVie immunology study, Study M13-093, as of 28 November 2015. Of the 935 subjects with CLL/SLL that have been treated in the venetoclax oncology clinical program: 336 patients have received venetoclax monotherapy and 599 have received venetoclax in combination with other agents including rituximab, obinutuzumab, and bendamustine.

The most common adverse events (incidence >20%) reported for all subjects in CLL/SLL monotherapy studies were diarrhea (40.2%), neutropenia (38.7%), nausea (37.8%), fatigue (27.4%), upper respiratory tract infection (26.5%), and anemia (25.3%). The most common Grade 3 and above adverse events were neutropenia (36.0%), anemia (14.6%), and thrombocytopenia (13.1%). The most common serious adverse events were pneumonia (5.7%), febrile neutropenia and malignant neoplasm progression (5.7% each). The safety profile in combination studies is consistent with that observed in monotherapy studies and with known toxicity profile of combination agents.

In combination with rituximab, serious adverse reactions were reported in 46% of patients, with the most frequent (\geq 5%) being pneumonia (9%). The most common adverse reactions (\geq 20%) of any grade were neutropenia (65%), diarrhea (40%), upper respiratory tract infection (39%), fatigue (22%), cough (22%), and nausea (21%).

Tumor lysis syndrome (TLS) is an important risk, particularly in subjects with CLL. Tumor lysis syndrome, including fatal events and renal failure requiring dialysis, have occurred in previously treated CLL patients with high tumor burden when treated with venetoclax. As a result of on-target effects, the potential for TLS with venetoclax was identified early in the program when the initial 3 subjects with relapsed/refractory CLL/SLL received starting doses of 100 mg or 200 mg and experienced TLS, which was reported as an adverse event for each. The starting dose was reduced to 20 mg and prophylaxis and monitoring instituted, with 3 week ramp-up.

Subsequently, 2 fatal events in the setting of TLS and another event of clinical TLS in subjects with CLL/SLL occurred in December 2012. After comprehensive review of all safety data available from studies with venetoclax, a revised dosing regimen with a ramp-up period of 5 weeks (starting from 20 mg) and enhanced TLS prophylaxis and monitoring measures were implemented in all CLL studies. A subsequent analysis of data from subjects with CLL/SLL following the implementation of prophylaxis measures, who completed monotherapy, indicated a marked reduction in severity and frequency of TLS when compared to the previous analysis. None of the subjects experienced any serious (including fatal) or non-serious event of clinical TLS (CTLS) or had study treatment discontinued because of TLS. Overall, the clinical data strongly support that the risk of TLS with venetoclax in CLL/SLL subjects is highest when initiating venetoclax dosing, especially with a higher initial dose of venetoclax, as well as being greater in subjects with a large tumor burden.

The earlier clinical trials identified risk factors for tumor lysis syndrome. The risk of TLS is a continuum based on multiple factors, including tumor burden and comorbidities. Reduced renal function (CrCl <80 mL/min) further increases the risk. In addition, measurements of tumor burden, including maximum lymph node diameter and absolute lymphocyte count define TLS risk.

Subjects have been classified in 3 risk categories based on risk for developing medically concerning TLS with venetoclax administration. The tumor burden assessed by the nodal disease and absolute lymphocyte count has been used to defined each category as below:

Tumor Burden Category	Criteria
Low	All measurable lymph nodes with the largest diameter < 5 cm by radiologic assessment AND ALC < 25k/uL
Medium	Any measurable lymph node with the largest diameter >/= 5 cm but < 10 cm by radiographic assessment OR ALC >/= 25k/uL
High	Any measurable lymph node with the largest diameter >/= 10 cm by radiologic assessment OR

ALC >/= 25k/uL AND any measurable lymph node with the
largest diameter >/= 5 cm

Patients should be assessed for risk and should receive appropriate prophylaxis for TLS, including hydration and anti-hyperuricemics. Changes in blood chemistries consistent with TLS that require prompt management can occur as early as 6 to 8 hours following the first dose of venetoclax and at each dose increase. Venetoclax prescribing information include standard of care recommendations for monitoring of blood chemistries, and use of more intensive measures (intravenous hydration, frequent monitoring, and hospitalization) as overall risk of TLS increases (see Appendix D and E: Prophylaxis and Management of TLS).

Grade 3 or 4 neutropenia occurred in 41% (98/240) of patients treated with venetoclax in the pivotal previously treated CLL 17p deletion study. Monitor complete blood counts throughout the treatment period. Interrupt dosing or reduce dose for severe neutropenia. Consider supportive measures including antimicrobials for signs of infection and use of growth factors (eg, G-CSF). In addition, 49 patients with CLL were treated with venetoclax + rituximab in a phase 1 M13-365 clinical trial. The rate of neutropenia (grade 3 and above) was 53.1%.

Do not administer live attenuated vaccines prior to, during, or after treatment with venetoclax until B-cell recovery occurs. The safety and efficacy of immunization with live attenuated vaccines during or following venetoclax therapy have not been studied. Advise patients that vaccinations may be less effective.

2.2.3.3 Summary of Clinical Efficacy of Venetoclax with Rituximab

The combination of venetoclax and rituximab was evaluated in a randomized, open-label, phase 3 trial. 389 patients were randomized to receive venetoclax for up to 2 years (from day 1 of cycle 1) plus rituximab for the first 6 months (venetoclax-rituximab group) or bendamustine plus rituximab for 6 months (bendamustine-rituximab group). The trial design did not include crossover. The primary end point was investigator-assessed progression-free survival.

The treatment regimen utilized the same dose escalation/ ramp-up strategy as utilized in early monotherapy trials. Rituximab was added on week 6, after completion of the ramp-up. Patients received rituximab 375 mg/m2 for the 1st dose, then 500 mg/m2 for 5 additional monthly doses.

After a median follow-up period of 23.8 months, the rate of investigator-assessed progression-free survival was significantly higher in the venetoclax-rituximab group (32 events of progression or death in 194 patients) than in the bendamustine-rituximab group (114 events in 195 patients); the 2-year rates of progression-free survival were 84.9% and 36.3%, respectively (hazard ratio for progression or death, 0.17; 95% confidence interval [CI], 0.11 to 0.25; P<0.001 by the stratified log-rank test). The benefit was maintained across all clinical and biologic subgroups, including the subgroup of patients with chromosome 17p deletion; the 2-year rate of progression-free survival among patients with chromosome 17p deletion was 81.5% in the venetoclax-rituximab group versus 27.8% in the bendamustine-rituximab group (hazard ratio, 0.13; 95% CI, 0.05 to 0.29), and the 2-year rate among those without chromosome 17p deletion was 85.9% versus

41.0% (hazard ratio, 0.19; 95% CI, 0.12 to 0.32). The benefit of venetoclax plus rituximab over bendamustine plus rituximab was confirmed by an independent review committee assessment of progression-free survival and other secondary efficacy end points.

The rate of grade 3 or 4 neutropenia was higher in the venetoclax-rituximab group than in the bendamustine-rituximab group, but the rates of grade 3 or 4 febrile neutropenia and infections or infestations were lower with venetoclax than with bendamustine. The rate of grade 3 or 4 tumor lysis syndrome in the venetoclax-rituximab group was 3.1% (6 of 194 patients). (8)

2.3 High Dose Methylprednisolone

Corticosteroids have long been used in regimens to treat B-cell malignancies. High dose methylprednisolone (HDMP) has been studied as a single agent in treatment of advanced CLL. A small study was conducted using high dose methylprednisolone at a dose of 1 gm/m2 daily for five days repeated every four weeks in subjects with chemotherapy refractory CLL (Thornton et al., 1999). In this study no complete responses were noted, however, 6 of 11 (55%) subjects had partial responses following, on average four cycles of treatment. In addition to improving the subjects' sense of well-being and reducing lymphadenopathy, treatment with HDMP was associated with marked improvement in hematological parameters including rise in hemoglobin and platelet counts indicating improved bone marrow function.

In vitro and in vivo data suggest that there is a synergistic effect of methylprednisolone and Rituximab (9). This is demonstrated by the fact that CLL cells lose the survival protection conferred by stromal cells and undergo apoptosis when incubated in the presence of methylprednisolone and Rituximab. Our preliminary data from a study in subjects refractory to fludarabine has shown that the combination of HDMP-Rituximab can be safely administered with no major Grade III or IV side effects. All treated subjects showed response to this treatment regimen when evaluated at two months after completion of treatment (4 subjects with complete response and 3 subjects with partial response). A long-term follow up analysis of those subjects has shown that the median time to progression is 18 months, which is unexpectedly high in this group of fludarabine refractory CLL subjects.

In addition, the combination of HDMP-Rituximab in previously untreated subjects has been evaluated. (9) A total of 28 subjects with a median age of 65 years were enrolled in this study. Subjects received HDMP at 1 g/m2 each day for 3 days during each of the three 4-week cycles together with rituximab and prophylactic antimicrobial therapy. The treatment was well-tolerated and the main toxicities were Grade ≤ II and included, hyperglycemia, insomnia, fluid retention. We also observed 2 transient episodes of grade III-IV toxicity secondary to infection, resulting in pneumonia or sinusitis that resolved completely after antibiotic treatment. The overall response rate was 96% (N=27). Nine subjects (32%) achieved a complete remission (CR), two of which were without detectable minimal residual disease (MRD). Six subjects with MRD received consolidation with alemtuzumab; five of these subjects achieved an MRD-negative CR. With over 3 years of follow-up median progression-free survival was 30.3 months with only 39% of subjects requiring additional therapy, and an overall survival that was 96%. Most subjects showed normalization of the absolute lymphocyte count after the first cycle of treatment as well as rapid

recovery of cytopenias. Pharmacodynamic studies showed that leukemia cells from subjects responding to this combination regimen were induced to express pro-apoptotic molecules, such as Bid, Apaf-1, Smac-Diablo, and to down regulate expression of anti-apoptotic molecules, such as XIAP and McI-1.

2.4 Study Rationale

The combination of venetoclax and rituximab is an effective and FDA-approved regimen to treat patients with CLL or SLL who have previously received treatment, though brings risk of tumor lysis syndrome (TLS) upon initiation of venetoclax. This risk is currently mitigated by careful prophylactic and monitoring measures during the initiation of venetoclax, including inpatient hospitalization and serial lab monitoring for patients who have a high tumor burden. Further mitigating the TLS risk will improve this treatment.

This risk of TLS is associated with the amount of tumor burden, and patients with Low Tumor Burden (absolute lymphocyte count less than 25k/uL; all lymph nodes less than 5 cm in diameter) are considered to have low TLS risk, and can be monitored without hospitalization (Venetoclax prescribing information). Therefore, decreasing the CLL tumor burden prior to initiation of venetoclax can also be a risk mitigation strategy.

The combination of High-Dose Methylprednisolone (HDMP) and rituximab has been evaluated as a treatment for patients with CLL. For patients with fludarabine-refractory CLL, the ORR was 96%, the CR rate was 36%, and all patients would have met the above criteria for Low Tumor Burden at the completion of therapy. The ALC values reduced in majority of patients within the 1st cycle. Therefore, HDMP + Rituximab is an ideal potential debulking strategy prior to initiation of venetoclax based on the following rationale:

- high rate of improvement of lymphadenopathy and lymphocytosis in previous publications.
- lack of added myelotoxicity; manageable overall toxicity profile compared to rituximab + venetoclax alone.
- administered in an outpatient setting.

3.0 Objectives

Purpose: to determine the feasibility of treating patients with HDMP + rituximab as a means of debulking prior to initiating venetoclax.

Objectives:

Primary:

1. To determine the percentage of patients who have a reduction of lymphadenopathy (from greater than to less than 5 cm in largest diameter) and/or absolute lymphocyte count (from greater than to less than 25k/uL) following 1 or 2 cycles of HDMP + rituximab (only 1 cycle permitted if subject enrolled after protocol v5 approval).

Secondary:

- 1. To determine the rate of laboratory or clinic TLS with this strategy.
- 2. To determine the safety (CTCAE4) of this approach.
- 3. To determine the overall efficacy (iwCLL) of this overall strategy.
- 4. To determine the percentage of patients who have undetectable minimal residual disease in the bone marrow.

Endpoints:

Primary:

1. Percentage of patients that have a decrease in tumor burden from levels of disease that meet "Medium/High-tumor burden" criteria to "Low tumor burden" criteria for disease burden following a maximum of 2 cycles of HDMP + Rituximab (following a maximum of 1 cycle if subject enrolled after protocol v5 approval).

Secondary:

- 1. Percentage of patients that have a decrease in tumor burden from levels of disease that meet "Medium/High-tumor burden" to meet "Low tumor burden" criteria for disease burden following 1 cycle of HDMP + Rituximab.
- 2. Percentage of patients that have a decrease in tumor burden from levels of disease that meet "Medium/High-tumor burden" to meet "Low tumor burden" criteria for disease burden following 2 cycles of HDMP + Rituximab.
- 3. Rate of laboratory TLS (from start of treatment until completion of venetoclax ramp-up)
- 4. Rate of clinical TLS (from start of treatment until completion of venetoclax ramp-up)
- 5. Adverse events by CTCAE4 definitions
- 6. Overall Response rate, Partial Response rate, and Complete response rate per iwCLL criteria after 9 months of venetoclax and at completion of treatment.
- 7. Undetectable minimal residual disease (MRD) rate based on bone marrow biopsy after 9 months of venetoclax, and at completion of treatment.

4.0 Study Design

4.1 Description

This is a single center, open-label, pilot/feasibility study designed to evaluate the feasibility of HDMP/Rituximab as an approach to decrease TLS risk for patients who receive venetoclax for treatment of CLL/SLL.

Patients with CLL/SLL who require therapy, and have disease burden meeting criteria for Medium or High Tumor Burden (based on: lymph nodes >/= 5 cm in diameter and/or absolute lymphocyte count >/= 25k/uL) are enrolled.

- Patients will receive HDMP + Rituximab for 1 cycle, followed by reassessment of Tumor burden.
- Patients will then initiate venetoclax dose ramp-up, with ramp-up schedule according to venetoclax package insert.
- If Tumor Burden classification is still Medium/High after 1 cycle of HDMP + rituximab, patients are also given the option to repeat a 2nd cycle of HDMP + Rituximab prior to the venetoclax dose ramp-up.

Upon completion of ramp-up (venetoclax to 400 mg), all patients will continue Venetoclax 400 mg (or highest tolerated dose) for up to 2 years. Patients will also continue rituximab 500 mg/m2 q 28 days through Cycle 6.

4.2 Endpoint Assessment:

- 1. Assessment of the disease burden after a maximum of 2 cycles of HDMP + Rituximab is the primary endpoint for HDMP/R as an approach to decrease risk of TLS.
- 2. Assessment of the disease burden after 1 cycle of HDMP + Rituximab.
- 3. Assessment of the disease burden after 2 cycles of HDMP + Rituximab (for the subset of patients that do not meet criteria for low tumor burden after 1 cycle).
- 4. Clinical and laboratory TLS events between start of treatment and the completion of venetoclax dose-ramp up (Cycle 2, Day 1)
- 5. Presence or absence of detectable MRD in the marrow will be assessed after approximately 9 months of venetoclax and completion of treatment.
- 6. Radiology assessment after approximately 9 months of venetoclax and at the completion of therapy, and as clinically indicated (unless prior imaging studies are without measurable disease)

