7.1.2 Dosage and Administration

Only methylprednisolone sodium succinate should be used for intravenous administration.

HDMP will be administered at 1gr/m2 on Days 1-3 of cycles 0 (with optional repeat for subset of patients who do not greater than low-risk for TLS after 1 cycle). HDMP will be given over 90 minutes and subsequent to the completed infusion, the infusion of Rituximab will be initiated. It will be diluted on 0.9% normal saline and administered directly into a vein over 90 minutes.

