9.0 Statistical Considerations

9.1 General Considerations

This is a pilot/feasibility clinical trial, with the primary feasibility endpoint being debulking of tumor burden to meet criteria for low Tumor Burden upon the completion of cycle 0

.The primary efficacy endpoint is the percentage of patients that have a decrease in tumor burden from levels of disease that meet "Medium/High-tumor burden" criteria to "Low tumor burden" criteria for disease burden following a maximum of 2 cycles of HDMP + Rituximab (called cycle 0 in the protocol schedule of events).

Tumor burden will be assessed prior to initiation of therapy, and after each cycle of HDMP + Rituximab (maximum 2 cycles). See section 8.1 for the definition of these categories of tumor burden.

The secondary endpoints are as follows:

- Percentage of patients that have a decrease in tumor burden from levels of disease that meet "Medium/High-tumor burden" to meet "Low tumor burden" criteria for disease burden following 1 cycle of HDMP + Rituximab.
- Percentage of patients that have a decrease in tumor burden from levels of disease that meet "Medium/High-tumor burden" to meet "Low tumor burden" criteria for disease burden following 2 cycles of HDMP + Rituximab.
- Rate of laboratory TLS (from start of treatment until completion of venetoclax ramp-up).
 See Appendix B for definition and grading of TLS.
- Rate of clinical TLS (from start of treatment until completion of venetoclax ramp-up)

- Adverse events by CTCAE4 definitions and iwCLL definition for hematologic AEs (see section 10.0 for iwCLL definition of hematologic AE).
- Overall Response rate (ORR), Partial Response (PR) rate, and Complete response (CR) rate per iwCLL criteria after 9 months of venetoclax and at completion of treatment. See section 8.2 for iwCLL criteria for definitions of each level of response. ORR includes all patients who have either a PR or CR.
- Undetectable minimal residual disease (MRD) rate based on bone marrow biopsy after 9
 months of venetoclax, and at completion of treatment. Undetectable MRD is defined as
 less than 0.01% CLL cells.

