9.2 Sample size justification

Seventeen patients are enrolled to evaluate the primary endpoint. A success rate of 60% of patients adequately debulking (defined as having low Tumor Burden at the end of cycle 0) will be considered compelling, establishing the feasibility of this approach, and support further studies. A success rate of 30% would be not compelling for further studies. With 17 patients, the study is adequately powered to evaluate this. A Simon's two-stage minimax design is utilized, with stopping for futility if an insufficient number of patients are debulked by HDMP/Rituximab. This design will have 80% power to reject the null hypothesis at 4% significance level and conclude that the true debulking rate at cycle 0 is above 30%, if the observed rate is ≥60%. Note that if patients are still meeting med/high tumor burden, they may repeat cycle 0 once more.

The null hypothesis that the true debulking rate is 30% at Cycle 0 will be tested against a one-side alternative. In the first stage, 10 patients will be accrued. The study enrollment will be put on hold for interim analysis until the response results for Stage 1 patients are known. If there are 2 or fewer responses (patients achieving low Tumor Burden) in these 10 patients, the study will be stopped. Otherwise, 7 additional patients will be accrual for a total of 20. The null hypothesis will be rejected if 9 or more responses are observed in 17 patients.

Early stopping probability: Under this design, if the null hypothesis is true, the probability of stopping the trial early will be 38.3%. The sample size calculation was done using PASS version 14.0.3 (released September 22, 2015). Sample size calculation did not incorporate the safety endpoint. Statistics for safety outcomes will be presented descriptively.

Accrual and study duration

We expect to accrue 1-2 patients every month. All patients will be accrued within 12-24 months. Patients will be followed for 24 months. The total duration of this study will be about 36 months.

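### The v5 limit of one HDMP + rituximab cycle is stated in section 3.0 but was not carried into 4.1, 7.1.2, 9.2 or the primary endpoint wording elsewhere

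*Combined protocol and SAP*

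**What the plan says.** Section 3.0 states the limit twice. The primary objective adds "only 1 cycle permitted if subject enrolled after protocol v5 approval", and the primary endpoint adds "following a maximum of 1 cycle if subject enrolled after protocol v5 approval". Note (a) to the Cycle 0 part of Table 3 is garbled in the text available, but appears to say the same.

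Three places keep a repeat without that limit:
- Section 4.1, third bullet: for patients still Medium/High after one cycle, "patients are also given the option to repeat a 2nd cycle of HDMP + Rituximab prior to the venetoclax dose ramp-up".
- Section 7.1.2, on methylprednisolone: "with optional repeat for subset of patients who do not greater than low-risk for TLS after 1 cycle".
- Section 9.2, at the end of its first paragraph: "if patients are still meeting med/high tumor burden, they may repeat cycle 0 once more".

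The primary endpoint is also stated without the limit. Section 9.1 has "following a maximum of 2 cycles of HDMP + Rituximab (called cycle 0 in the protocol schedule of events", and 4.2 item 1 has the assessment "after a maximum of 2 cycles of HDMP + Rituximab is the primary endpoint for HDMP/R". In the synopsis, the primary objective and primary endpoint (row 3.1) refer to 1 or 2 cycles, and endpoint assessment item 1 (row 4.0) refers to a maximum of 2.

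The synopsis treatment plan, by contrast, already describes one cycle followed by the venetoclax ramp-up, and rituximab dosing in 7.2.2 mentions no repeat. The footer shown in the synopsis gives version 5, Dec-2024.

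**The concern.** The number of debulking cycles is both a treatment rule and part of the primary endpoint, so it should read the same wherever staff or analysts look it up. Here a clinician working from the design description would offer a post-v5 patient a second high-dose steroid and rituximab course that the objectives section rules out. If that patient then reached Low tumor burden, an analyst using 9.1 would count a success and an analyst using 3.0 would not. The document has no rule saying which section takes precedence.

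**Working it through.** **1. The plan's own figures.** Inputs from 9.2: null rate 30%, target rate 60%, 10 patients in stage 1, stop at 2 or fewer responses, 17 patients in all. The final rule is "The null hypothesis will be rejected if 9 or more responses are observed in 17 patients".

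- Early stopping = P(X1 ≤ 2), with X1 binomial (10, p). At p = 0.30: 0.0282 + 0.1211 + 0.2335 = 0.3828 (stated 38.3%).
- Rejection = sum over x = 3 to 10 of P(X1 = x) × P(X2 ≥ 9 − x), with X2 binomial (7, p). At p = 0.30 this is 0.0402 (stated 0.04). At p = 0.60 it is 0.8008 (stated 80%).

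All three agree with the plan. None depends on how the cycle limit is worded, so the fix leaves them alone.

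**2. The sections side by side, for a patient enrolled after v5 approval.**

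| Place | What it allows or counts | v5 limit stated? |
|---|---|---|
| 3.0 primary objective | 1 cycle only | Yes |
| 3.0 primary endpoint | Low after at most 1 cycle | Yes |
| 4.1, bullet 3 | Second HDMP + rituximab cycle | No |
| 7.1.2 | Optional repeat of HDMP | No |
| 9.2 note | Cycle 0 may be repeated once | No |
| 9.1 primary endpoint | Low after at most 2 cycles | No |
| 4.2 item 1 | Assessment after at most 2 cycles | No |
| Synopsis objective and endpoint | After 1 or 2 cycles | No |
| Synopsis endpoint assessment item 1 | After at most 2 cycles | No |

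The first three unrestricted rows permit what 3.0 excludes. The remaining four are incomplete rather than contradictory, because a patient who receives one cycle satisfies them. Nor does 9.2 settle the count: it defines success at the end of cycle 0, while 9.1 applies the name cycle 0 to up to two cycles.

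**3. What a second course under 4.1 contains.** Using the Cycle 0 doses in 6.2:
- methylprednisolone: 3 × 1,000 = 3,000 mg/m2
- rituximab: 100 mg + 3 × 375 mg/m2 = 100 mg + 1,125 mg/m2

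**4. How the count diverges.** Take a post-v5 patient who is Medium/High after cycle 1, is given a second course under 4.1, and is then Low. Under 9.1 this is a success; under 3.0 it is not. One such patient alters the final decision only if the 3.0 count is 8 of 17 (8/17 = 47.1%, against 9/17 = 52.9%). If the patient is in stage 1, the decision to continue is altered only if the 3.0 count is 2 of 10.

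**The case against.** The best defense is that a specific, dated restriction qualifies a general option. Section 3.0 says plainly that one cycle is permitted, the schedule note appears to repeat it, and the synopsis treatment plan has one cycle. On that reading 4.1, 7.1.2 and 9.2 simply describe patients enrolled before v5. The reading is reasonable, but none of those sections says so, and 4.1 and 7.1.2 are where treating staff would look.

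Several narrower points stand:
- Only 4.1 expressly offers the combined course. Section 7.1.2 covers HDMP alone, and the 9.2 sentence is a remark in a sample size paragraph.
- The two endpoint counts differ only after a patient has received a course that 3.0 does not permit.
- There may be no such patient. The synopsis plans one year of enrollment from Sept/2019 and a last visit in Sept/2023, before the Dec-2024 footer. These are estimates and the v5 approval date is not given, so the documents do not settle it.

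A reader might infer a stronger claim from the boundary probabilities. The chance of passing stage 1 and finishing at exactly 8 of 17 is 0.0635 at a true rate of 30%, 0.1857 at 45% and 0.1056 at 60%. These are chances of sitting at the boundary, not of a changed conclusion. A changed conclusion also needs a post-v5 patient who stays Medium/High, receives the excluded course, converts, and is counted under 9.1. The documents give none of those probabilities.

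A reader might also infer that second-cycle conversions inflate the type I error through this conflict. The documents do not support that: they give no second-cycle conversion rate, and for patients enrolled before v5, counting up to two cycles is what 3.0 intends.

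**Conclusion.** The point holds as an inconsistency left by an amendment that was only partly carried through, not as a questionable design choice. Three statements (4.1 bullet 3, 7.1.2, the 9.2 note) keep a repeat that 3.0 no longer permits for post-v5 patients; 4.1 is the operative one. Five statements of the primary objective or endpoint (9.1, 4.2 item 1 and three in the synopsis) omit the limit.

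Severity is modest, and the effect on the trial's result cannot be quantified from the documents. The conclusion assumes that 3.0 expresses the sponsor's current intention, which its explicit reference to v5 supports. The text should still be corrected, because it governs both permitted dosing and what counts as a success.

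**What to change.** - Add "only 1 cycle permitted if subject enrolled after protocol v5 approval" to the third bullet of 4.1, to 7.1.2 and to the repeat note in 9.2.
- Add "following a maximum of 1 cycle if subject enrolled after protocol v5 approval" to the primary endpoint text in 9.1 and 4.2 item 1, and to the synopsis primary objective, primary endpoint and endpoint assessment item 1.
- State that the secondary endpoint after 2 cycles and 4.2 item 3 apply only to patients enrolled before v5 approval. Both remain valid for them.

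The cost is a few phrases, mostly in the sponsor's own words. Sample size, decision rule and analysis stay the same. No new data are needed: enrollment date, set against the v5 approval date, identifies who is covered, and 9.6 already reports the number of HDMP + rituximab cycles.
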